### **7.11 Concomitant medication accepted**

A concomitant therapy is any drug or substance administered from the time of the subject’s written consent until the subject’s End of Study Visit.

Concomitant treatment with any of the following is allowed:

- Medications necessary for the treatment of AEs
- Any medications used to treat MS symptoms such as spasticity, bladder impairment, pain, or depression
- Short courses of iv high-dose corticosteroids as a rescue medication for exacerbations of MS
- Corticosteroids that are administered by non-systemic routes (e.g., topical, inhaled)

Any treatment which are continued during the study and/or initiated or changed during the study must be recorded in source data and in the CRF.

### **7.12 Prohibited Concomitant Therapy**

Concomitant treatment with any of the following is *not* allowed while receiving study treatment, unless as otherwise described in this protocol:

- Any non-study drug treatments directed toward the treatment of MS such as immunomodulatory treatments or chronic immunosuppressant therapy except tacrolimus
- Any investigational product, including investigational symptomatic therapies for MS and investigational therapies for non-MS indications

-Systemic steroid therapy including, but not limited to, oral corticosteroids (e.g., prednisone) or periodic (e.g., monthly) treatment with IV methylprednisolone, except for protocol-defined treatment of relapses as described above and course of oral prednisolone at the above mentioned dosage in the first 25 days after hNPCs injection.

Subjects who receive any of these restricted treatments may be required to permanently discontinue study treatment.

### **7.13 Other medical procedures**

All the routinely procedures used in MS patients are allowed.

## 8 Overall design

### 8.1 Sample size

Will be enrolled max 24 patients.

### 8.2 Protocol schedule and timelines

Anticipated start of recruitment: **April, 2017**

Anticipated stop of recruitment: **March 2018** or **study termination**

End of total follow-up: **When all subjects have completed the 96 weeks follow up period or terminated the study**

Draft statistical report 3-4 months after the end of total follow-up

Integrated final report 6 months after the end of total follow-up

### 8.3 Study Procedure and Study Flow-chart

#### 8.3.1 Enrolment phase

Is the process of informed consent signature (described in the ethical consideration chapter). Starting from the signature of the informed consent by the patient or patients' legal tutors, the subjects will be enrolled in the clinical trial. When the enrolment is confirmed the patient screening number will be assigned consecutively in increasing order starting with '001'. The list will be filed with the investigator's file. After the enrolment of a patient in the study, the investigator sends the enrolment module to the principle investigator by fax or email to clinical research monitor.

Those protocol phases are foreseen after signature of the informed consent:

- **Screening/baseline phase**, during which the conditions required by the clinical protocol for patients' inclusion/exclusion will be assessed (screened subject). The duration will be of three weeks (+/- 3 working days). At the end of the screening phase, the inclusion/exclusion criteria of the study will be evaluated (enclosed subject).
- **Pre-treatment phase**: carried from the end of the screening phase to the day before the start of treatment.
- **Treatment phase**: The intrathecally administration of hNPCs will be performed on day 0. Prophylactical treatment with Tacrolimus will be performed for 96 weeks starting from day -7 whereas oral corticosteroids will be administered for the first 4 weeks.
- **Follow-up phase**: 96 weeks after the experimental drug administration day 0.

At the end specify if the end of total follow-up or single patient follow-up.

At the end of the total follow-up, for all patients enrolled and treated in the study is planned a long term follow up, in accordance with the national applicable laws and the international guidelines.

**8.3.2 Screening Phase**

All subjects must sign informed consent prior to conduct any study specific procedure. All the inclusion criteria and none of the exclusion criteria listed above respectively, must be satisfied. Following consent, all these evaluations will be performed within the screening phase three weeks (+/- 3 working days):

- Record of general medical and MS history with concomitant medication revision
- Inclusion Criteria and Exclusion criteria evaluation
- Physical examination
- Record of vital signs (blood pressure, heart rate, O2 saturation, temperature, weight, height)
- Hematological visit
- Haematological blood tests\_comprehensive of:
  - Complete blood count\*, extensive clinical laboratory evaluations\*\*,
  - \*Hemoglobin, Platelets, Leukocytes, Neutrophils, Lymphocytes, Monocytes
  - \*\*PCR, LDH, Total Protein, albumin, IgG, IgA, IgM, AST, ALT, GGT, ALP, Na+, K+, Ca++, BUN, uric acid, Total Bilirubin, Direct Bilirubin, Glucose, creatinine, creatinine clearance, ferritin, Serum Iron, transferrin, transferring saturation, INR, PTT
- Infections screening: HBs-Ag, HBs-Ab, HBe-Ag, HBc-IgG, HBc-IgM, HBV-DNA, HCV-Ab, HCV-RNA, HIV-Ab, VZV-IgG, VZV-IgM, HSV1-IgG, HSV1-IgM, EBV-IgG, EBV-IgM, EBV-DNA, CMV-IgG, CMV-IgM, CMV-DNA, Toxo-IgG, Toxo-IgM, HSV2-IgG, HSV2-IgM, Galactomannan detection
- Vitamin B12 and folats evaluation
- TSH evaluation
- Blood group
- Serum pregnancy test (if applicable)
- Immunological analysis
- Electrocardiogram
- Chest Rx
- Abdominal ultrasound
- Neurological examination comprehensive of EDSS scale, T25FW, 9HPT, SDMT
- Neurophysiological assessment (OCT, VEP, SEP, MEP)
- Brain and Spinal cord MRI

After the patient inclusion the investigator sends the enrolment module to the clinical research module. When the inclusion is confirmed the patient definitive number will be assigned as follow:

Patient number for monocentric trial (UPN)					
Screening number			Inclusion number		
0	0	1	0	0	1

### 8.3.3 Pre-treatment phase

This phase will start after the ending of all the procedure of the screening/baseline phase and it will end the day before the treatment phase (day-1):

#### Day 1 of pretreatment phase (Friday):

- Inclusion/exclusion criteria revision
- Record of vital signs (blood pressure, heart rate, O2 saturation, temperature, weight, height)
- AEs, SAEs record
- Tacrolimus administration at 0.05 mg/kg twice daily
- Acyclovir, co-trimoxazole and pholates from the beginning of tacrolimus as prophylactic medication
- Haematological evaluation
- Physical examination
- Pharmacological surveillance of FK506 through blood sample will be performed after three (Monday) and seven days (Friday). This procedure will be performed till the tacrolimus will reach the therapeutical range. Haematological blood test comprehensive of: complete blood cell count, blood chemistry and urin analysis: PCR, AST, ALT, GGT, Na+, K+, Ca++, Total Bilirubin, Direct Bilirubin, Glucose, creatinine, creatinine clearance, LDH, PT, PTT (will be performed seven days after the beginning of tacrolimus)

#### Day -1

- Neurological examination comprehensive of EDSS scale
- Vital signs
- AEs, SAEs record
- Relapse Assessment
- Concomitant medication revision
- Haematological blood examination: complete blood cell count, blood chemistry: will be performed if not performed within seven days
- Prednisone (Deltacortene) administration (50 mg)

At the end of all these assessment, patients will be assigned to one of the four different cohort of treatment (A-D) (see chapter Methods of assigning patients to treatment groups).

### 8.3.4 Treatment Phase

On day 0 patients will undergo pharmacological surveillance of FK506 through blood sample. IV Methylprednisolone at the dosage of 125 mg will be administer one hour prior to lumbar puncture.

They will received intrathecally hNPCs through lumbar puncture in an hospitalized setting and the patients will be monitored for at least 24 hours. Before the injection, hNPCs will be thawed and DMSO will be carefully washed out; hNPCs will be than resuspended in 10 cc of saline solution.

CSF examination cohprehensive of chemicophysical and infectivological will be performed.

Body temperature, blood pressure, heart rate and oxygen saturation will be measured at baseline and after 15, 60, 180 minutes and then before discharge. Any toxicity will be treated at the discretion of the treating neurologist.

### 8.3.5 Follow-up Phase

The follow-up phase will have a duration of 96 weeks. However the patients we'll be followed for the further 6 years at least.

Patients will attend control visits weekly for the first 4 weeks after hNPCs administration and then at 8 and 12 weeks. Starting from 12 weeks visits will be performed every 12 weeks. The procedures of each visit are described in details in the flow chart.

During the follow-up phase patients will receive tacrolimus, acyclovir, co-trimoxazole and folates for the entire follow-up (till week 96) and oral prednisone for 4 weeks.

The patient will undergo:

- Neurological visit with EDSS at week 4, 12, and then every scheduled visit
- T25FW, 9-HPT, SDMT at week 24, 48, 72, 96
- Haematological visit at week 4, 12, and then every scheduled visit
- General physical examination at every scheduled visit
- Record of vital signs at every scheduled visit
- AEs, SAEs record- Relapse Assessment at every scheduled visit
- Concomitant medication revision at every scheduled visit
- **Haematological blood tests comprehensive of:**

Complete blood count, extensive clinical laboratory evaluations will be performed at week 4, 12, 24, 48 and 96

Complete blood tests and biochemistry, urinalysis evaluation will be performed at week 2, 8, 36, 60, 72 and 84

Complete blood count evaluation will be performed at week 16, 20, 30, 42, 54, 66, 78 and 90

- Infectivological screening: CMV-DNA, EBV-DNA, Galactomannan detection will be performed at week 4, 12, 24, 48 and 96
- Immunological analysis: will be performed at week 4, 12, 24, 48 and 96
- Whole blood levels of tacrolimus will be obtained as reported in the specific section, in order to maintain a target of 5-10 ng/ml.
- CSF examination will be performed at week 12. During this visit the patient will be admitted to the hospital in the morning and will be discharged the day after (24 hours of observation after procedure). Complete chemico-physical evaluation, oligoclonal bands detection, CSF Cell evaluation, virological screening, ddPCR assays.
- Electrocardiogram, Chest Xray will be performed at visit week 48 e 96 and abdominal ultrasound only at visit 96
- Brain and spinal cord MRI at week 12, 24, 48 and 96
- Neurophysiological assessment (OCT, VEP, SSEP, MEP) will be performed at week 24, 48 and 96
- Administration of MsQuol54 will be performed at 12, 24, 48, 72 and 96 weeks

Additional visits will be planned if necessary. Specifically unscheduled visits will be performed in case of new or worsening symptoms related to the disease to exclude a relapse or in case of any adverse event not related to the disease.

**END OF STUDY VISIT:**

This visit will be performed 8 week after the end of treatment visit.

The patient will undergo:

- Neurological visit with EDSS
- Haematological visit
- General physical examination
- Record of vital signs
- AEs, SAEs record- Relapse Assessment
- Concomitant medication revision
- Haematological blood tests\_comprehensive of: Complete blood tests and biochemistry, urinalysis evaluation
- Infectivological screening: CMV-DNA, EBV-DNA, Galactomannan detection
- Administration of MsQuol54

**UNSCHEDULED VISIT:**

In case of clinical, neurological deterioration or every systemic new symptom not due to MS an unscheduled visit will be performed. During this visit the following procedure might be performed, at investigator discretion:

- complete neurological and general examination
- Haematology and biochemistry examination complete of ESV e CRP, CMV DNA, EBV DNA will be determinate every 24 weeks
- Chest Xray
- Brain and spinal cord MRI with gadolinium
- Lumbar puncture

**MS RELAPSE VISIT**

The assessment, management and reporting of MS relapse is made by the Primary Treating Physician.

MS relapse definition: appearance of a new neurological abnormality or worsening of previously stable or improving pre-existing neurological abnormality, separated by at least 30 days from onset of a preceding clinical demyelinating event (McDonald et al. 2001). The abnormality must have been present for at least 24 hours and occurred in the absence of fever (< 37.5°C) or known infection. MS relapse is defined as: any perceived change in symptoms or signs that persist for ≥ 48 hours in the absence of flu or fever and that is accompanied by objective changes on EDSS functional subscores (FSS) that leads to either a 1.0 point change in EDSS (for baseline EDSS 3 - 5.0) or a 0.5 change (for baseline EDSS ≥ 5.5) together with FSS changes of 2 points in any one FSS or 1 point in any 2 FS. Only relapses meeting the protocol definition will be considered as measure of efficacy.

Diagnosing MS relapses during the study: Patients will be instructed to immediately contact the Primary Treating Physician if he/she develops new or re-occurring or worsening neurological symptoms. If a patient reports new neurological symptoms or worsening of previous symptoms, an unscheduled visit is to be planned as soon as possible, ideally within 7 days. During this visit, the treating physician will first assess whether the new/worsening neurological abnormality is consistent with the definition of MS relapse above.

If so, the standard neurological examination (for the EDSS score) should be performed by the Independent EDSS Rater. If there is any doubt in the opinion of the treating physician, the default must always be to refer the case to the Independent EDSS Rater to perform an EDSS rating.

Confirmation of MS relapse: the definition of a confirmed MS relapse is one accompanied by a clinically relevant change in the EDSS performed by the Independent EDSS Rater, i.e. an increase of at least 0.5 points on the EDSS score, or an increase of 1 point on two FSs or 2 points on one FS, excluding changes involving bowel/bladder or cerebral FS compared to the previous available rating (the last EDSS rating that did not occur during a relapse).

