#### b) MID TERM (day 1-day 14)

- overall survival
- overall safety and tolerability measured by AE recording
- changes in neurological conditions not related to disease

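### Section 8.3.5 gives conflicting rules for an MS relapse (24 h against 48 h; EDSS 'and' against 'or' functional-system change) and does not say which applies

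*Combined protocol and SAP*

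**What the plan says.** The MS relapse visit text in section 8.3.5 contains three rules.

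- **24 h text.** A new or worsened neurological abnormality, at least 30 days after the previous event, without fever or known infection: "The abnormality must have been present for at least 24 hours". No EDSS or FS threshold is attached.
- **48 h text.** The next definition is "any perceived change in symptoms or signs that persist for ≥ 48 hours in the absence of flu or fever". It needs an EDSS change, which is 0.5 points when baseline EDSS is 5.5 or more, "together with FSS changes of 2 points in any one FSS or 1 point in any 2 FS".
- **Confirmation step.** The independent rater confirms a relapse on "an increase of at least 0.5 points on the EDSS score, or an increase of 1 point on two FSs or 2 points on one" functional system. Bowel/bladder and cerebral systems do not count. The 48 h text has no such exclusion.

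The section states one use for the result: "Only relapses meeting the protocol definition will be considered as measure of efficacy". It also tells the treating physician to check the event against the relapse definition given above. Neither reference says which text is meant.

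Relapse matters in two other places. Section 5.6 does not count an EDSS rise as disability progression if it is attributable to relapse. Section 5.3 lists "changes in neurological conditions not related to disease" as a primary endpoint item for 0-24 hours and for days 1 to 14, and section 5.5.1 asks the investigator to decide between an MS relapse and another, non-MS neurological disorder.

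**The concern.** A rule that decides which events count has to give one answer for a given event. Here the duration requirement doubles between adjacent definitions, the EDSS/FS requirement goes from absent to 'and' to 'or', and an FS exclusion appears only at the last step.

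Two results depend directly on the answer: the relapses used as a measure of efficacy, and the proportion free of disability progression at week 96. A third can depend on it indirectly. If an investigator uses section 8.3.5, the only place where relapse is defined, to call an early deterioration a relapse, that event leaves the neurological item of the short- and mid-term primary endpoints.

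The trial is open label and uncontrolled. If the choice between texts is left until events have occurred, it will be made with the events in view.

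**Working it through.** There is no plan figure to reproduce: the trial is descriptive and relapse has no assumed rate. The check is to apply each rule to every type of event.

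**Which branch applies.** Section 6.1 requires EDSS of at least 6.5. The 1.0-point branch of the 48 h text covers baseline EDSS 3 to 5.0 and so fits no patient at entry. The 0.5-point branch, with its attached FS condition, applies to everyone, and so does the and/or conflict.

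**Patterns.** Duration (under 24 h, 24 to under 48 h, 48 h or more) × EDSS rise of at least 0.5 (no, yes) × FS criterion met (no, yes) gives 3 × 2 × 2 = 12. Assumptions: no fever or infection, the 30-day separation is met, and the bowel/bladder and cerebral exclusion is ignored.

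The four patterns under 24 h are not relapses under either definition. The other eight are:

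| Duration | EDSS rise | FS met | 24 h text | 48 h text | Confirmation criterion met | Confirmed from 24 h text | Confirmed from 48 h text |
|---|---|---|---|---|---|---|---|
| 24 to <48 h | no | no | yes | no | no | no | no |
| 24 to <48 h | no | yes | yes | no | yes | yes | no |
| 24 to <48 h | yes | no | yes | no | yes | yes | no |
| 24 to <48 h | yes | yes | yes | no | yes | yes | no |
| ≥48 h | no | no | yes | no | no | no | no |
| ≥48 h | no | yes | yes | no | yes | yes | no |
| ≥48 h | yes | no | yes | no | yes | yes | no |
| ≥48 h | yes | yes | yes | yes | yes | yes | yes |

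**Results.**

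- Base definitions: 8 of 12 against 1 of 12. The one is among the eight, so they disagree on 8 − 1 = 7.
- After confirmation: 6 against 1, so they disagree on 6 − 1 = 5.
- Among events of 48 h or more, the 'and' rule accepts 1 of 4 EDSS/FS patterns and the 'or' rule 3 of 4. On this point confirmation is looser than the 48 h definition it would confirm.
- On FS exclusions the direction reverses. An FS change confined to bladder function satisfies the 48 h text but does not count as an FS change at confirmation.

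**A concrete case.** A patient has a sustained EDSS rise of 0.5 without the required FS change. This can happen because section 5.6 says EDSS combines FS scores with ambulation. Starting from the 24 h text it is a confirmed relapse. Under the 48 h text it is not a relapse. If the rise is still present at least 12 weeks later, the first reading lets it be set aside as relapse and the second leaves it to count as disability progression.

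**The case against.** **The section describes a sequence.** The physician screens against a definition, then the rater confirms, so 'or' belongs to confirmation and is not a rival definition. That is fair, and an FS-only episode does not become a relapse through the confirmation step alone. But the sequence still needs a starting definition, and two are given. The 5 disagreements remain with confirmation applied to both.

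**The duration conflict matters little for progression.** This stands. Progression must be confirmed at least 12 weeks later, so an episode that resolves within 48 hours cannot be progression under either text. Only the EDSS/FS wording matters there.

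**A reader might infer that the conflict decides what is disease and what is a safety event, or that it lets cell-related harm be hidden as MS.** The documents do not support that.

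- Section 8.3.5 states only an efficacy use. Section 5.5.1 leaves attribution to the investigator and does not cite the relapse definition.
- Section 5.5.7 records all adverse events whatever their relationship, and adverse event recording is itself a primary endpoint item in all three time windows.
- The dose-limiting toxicity rule in section 7.10 turns on grade and possible relation to the cells or the procedure, with no exemption for relapse. Relapse could be offered as an alternative explanation under the attribution terms of section 5.5.3.1, but that is a judgement on each event.
- The item for day 15 to week 96 has no disease exclusion.
- In the 0-24 h window an event starting after injection cannot yet have lasted 24 or 48 hours, so a relapse label there could only be retrospective.

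**A reader might also express the effect as one patient in 24.** No proportion of patients with neurological change is defined among the primary endpoints, so there is no such figure to move.

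**Conclusion.** The relapse rule is wrong as written, not merely short of detail: the same event is a relapse under one sentence and not under the next, and the text that should settle it points to neither.

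The size is logical, not numerical: 7 of 12 event types are classified differently by the two definitions, and 5 of 12 after confirmation. The documents give no relapse rate from which to estimate how many events would be affected. The counts rest on the assumptions stated with them, chiefly that the FS exclusion is ignored.

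The direct reach is relapse as a measure of efficacy and the week-96 progression-free proportion. The indirect reach, through investigator attribution, is one neurological item in the 0-24 h and day 1-14 primary endpoints. It goes no further into the safety results. Because the repair is cheap and should precede any look at the events, it should be made.

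**What to change.** Reconcile the MS relapse visit text in section 8.3.5 to one operative definition: one duration, one and/or rule for EDSS and FS change, and one set of FS exclusions, consistent with the confirmation step. Label it as the protocol definition and cross-refer to it from sections 5.5.1 and 5.6. The sponsor chooses the thresholds; this review takes no position on which are clinically right.

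Add a sentence that meeting the relapse definition does not by itself make an event unrelated to hNPCs or to the procedure.

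Do not add the converse rule, that every neurological change failing the definition is unrelated to disease. Section 6.1 admits patients with progressive MS, EDSS of at least 6.5 and a rise of at least 0.5 in the last 12 months. Worsening without relapse is expected in them, and such a rule would turn ordinary progression into a safety event.

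The cost is protocol wording. No visit, assessment or patient is added.

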## 9 Ethical and Regulatory Considerations

### 9.1 Regulatory and ethical compliance

This clinical study was designed, shall be implemented, conducted and reported in accordance with:

- the ethical principles laid down by the 18th World Medical Assembly (Helsinki, 1964) and all applicable amendments laid down by the World Medical Assemblies;
- the International Conference on Harmonization (ICH) Harmonized Tripartite Guidelines for Good Clinical Practice (GCP);
- all international laws and regulations;
- all national laws and regulations of the country(ies) in which the clinical trial is performed;
- all international or national applicable guidelines.

